10.7 Sample Size

Software nQuery Advisor 7.0 is used for sample size determination in this study.

As suggested by FDA during the type C meeting on 13Aug2014, and as also reinforced and documented in the official meeting minutes issued by FDA on 24Sep2014, this study needs to demonstrate 1) a significant improvement in diagnostic performance endpoints, i.e., sensitivity/specificity from unenhanced stress imaging (UE-DSE) to contrast-enhanced stress

imaging (CE-DSE) in term of detection and exclusion of CAD, and 2) lower the CI of CE-DSE sensitivity and specificity greater than 50% (a rate greater than chance).

For significant improvement in diagnostic performance endpoints, the null hypothesis is that there is no difference in sensitivity/specificity between CE-DSE and UE-DSE at peak stress; the alternative hypothesis is that CE-DSE is superior to UE-DSE in terms of higher sensitivity/specificity:

$$H_0: \text{Diag}_{\text{CE}} - \text{Diag}_{\text{UE}} = 0,$$

$$H_a: \text{Diag}_{\text{CE}} - \text{Diag}_{\text{UE}} > 0;$$

where Diag_{CE} and Diag_{UE} denote sensitivity/specificity for CE-DSE and UE-DSE at peak stress respectively.

With 2-sided significance level (alpha) of 5%, and the probability of a Type II error (β) of 0.20, assuming expected difference between CE-DSE and UE-DSE is 25%,¹ and the proportion of discordant pairs is 40%, 45 subjects will be needed for sensitivity/specificity respectively.

For lower CI of CE-DSE sensitivity/specificity greater than 50%, assuming sensitivity/specificity of CE-DSE = 65%, about 45 CAD positive subjects are needed to have 95% confidence that the lower limit of sensitivity >50%, and 45 CAD negative subjects are needed to have 95% confidence that lower limit of specificity >50%.

Assuming approximately 30% of subjects enrolled will be CAD positive,¹³ in order to obtain 45 CAD positive subjects, 150 subjects in total need to be enrolled. With a total of 150 subjects enrolled, this will also provide more than enough CAD negative subjects according to the above calculations. The prevalence of positive subjects will be tracked based on on-site CAD diagnosis from the truth standard and if less than 30% of subjects are CAD positive, additional subjects will need to be enrolled to obtain sufficient CAD positive subjects.

For the co-primary endpoint of critical shift from suboptimal at UE-DSE images to adequate images at CE-DSE, sample size assumptions are based on the results from the previous pivotal phase III Bracco-sponsored study (██████████).²² This study had 44.8%-46.0% of the subjects converted from suboptimal at UEUS to adequate at LUMASON-enhanced echocardiography (CEUS) at rest. When the sample size is 150, a 2-sided 95% CI for a single proportion using the large sample normal approximation will extend 8% from the observed proportion for an expected proportion of 45% subjects with critical shift from suboptimal at UE-DSE images to adequate images at CE-DSE. This can be translated as lower limit of 95% CI >35% for the observed proportion of subjects with critical shift.

Considering approximately 15% of subjects enrolled are anticipated to dropout, approximately 175 subjects will need to be enrolled.

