Stress echocardiography is an established imaging modality for the detection of coronary artery disease (CAD).^{1,2,3,4,5,6,7} The primary indication for conventional stress echocardiography is to indirectly detect angiographically significant ($\geq 50\%$ diameter) stenoses by inducing ischemia or to assess the patient's risk for a cardiac event.^{5,8,9,10} Increasingly stress echo techniques have been shown to offer valuable prognostic information in the risk evaluation of stable chronic CAD.^{5,10,11} Significant studies (> 100 patients) of dobutamine stress echocardiography (DSE) show a range for sensitivity of between 61–95%, while that for specificity ranged from 51–95%¹¹ for the diagnosis of CAD.¹ The detection of CAD with stress echocardiography is based on the observation of contractile dysfunction in any myocardial segment at rest or with stress; therefore, complete visualization of all left ventricular (LV) endocardial borders (EB) is necessary to document or exclude abnormalities of regional myocardial wall thickening confidently.^{12,13} Interpretation of wall thickening is qualitative, highly dependent on the skill and experience of the reviewing physician, and is affected considerably by quality of endocardial border delineation (EBD).^{12,13} Numerous patient factors may produce suboptimal images with poor EBD. Given, in addition, the challenges imposed by excessive cardiac motion due to hyperventilation and tachycardia at peak stress, non-diagnostic or poor-quality images may occur in up to 30% of patients.^{12,13} The advent of digital side-by-side analysis, standardized reporting criteria, and generalized use of tissue harmonic imaging has reduced, but not overcome, this problem.¹²

Use of ultrasound contrast agents (UCAs) has shown to improve EBD during stress echocardiography and is recommended for use in patients with poor unenhanced image quality by both the American Society of Echocardiography (ASE) and the European Association of Echocardiography (EAE).^{12,13} However, while Lumason™ (sulfur hexafluoride lipid-type A microspheres) with an approved trade name in the USA/SonoVue® (sulfur hexafluoride microbubbles) with an approved trade name for everywhere else in the world referred to hereafter as LUMASON, is approved for use in echocardiography both at rest and stress in the

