The muscle and cavity of the LV will be divided into 17 segments (17-segment model). The 17-segment model will be utilized as recommended by the ASE guidelines.^{1,12,27} The standard views of a 2D echocardiogram as defined by the ASE are all used as part of a 2D echocardiogram at rest and stress.²⁶ The clinical utility of improvement in LV EBD resulting from opacification of the LV as an aid in determination of more clinically relevant parameters is recognized by the 2008 ASE consensus statement as leading to improvement in feasibility, accuracy, and reproducibility of echocardiography for the qualitative and quantitative assessment of LV structure and function.¹²

Unevaluable image are defined as images with inadequate visualization of segments comprising all coronary artery territories due to 1 or more of the following artifacts: motion artifacts, lateral wall drop out, swirling or attenuation artifacts. From the published literature⁶ and previous Bracco-sponsored study²⁵ 8% of the UE-DSE images are expected to be unevaluable.

Stress can be induced by either physical exercise or pharmacologic agents. Physical stress was the first reported and used form of stress echocardiography, but it has several disadvantages since during exercise it is not possible to perform close echocardiographic monitoring and recordings are not reliable because of hyperventilation. Pharmacologic stress overcomes these disadvantages.

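### Section 10.7 gives 80% power for the superiority test alone; its own two inputs, taken together, give about a 55% chance that one reader meets both sensitivity conditions of 10.6.4

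*Combined protocol and SAP*

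**What the plan says.** Section 10.7 contains two separate calculations for the first co-primary endpoint.

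- **Superiority of CE-DSE over UE-DSE.** The inputs are "With 2-sided significance level (alpha) of 5"%, "the probability of a Type II error (β) of 0.20", "assuming expected difference between CE-DSE and UE-DSE is 25"%, and "the proportion of discordant pairs is 40%, 45 subjects will be needed for sensitivity/specificity respectively". No level is given for either examination.
- **Floor of 50% for CE-DSE.** The input is "assuming sensitivity/specificity of CE-DSE = 65"%, with the result that "about 45 CAD positive subjects are needed to have 95% confidence that the lower limit of sensitivity >50"%. The same number is given for CAD-negative subjects and specificity. No power is attached to this condition.

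Section 10.6.4 then joins the two: at least two of three blinded readers must show superiority, and the same two must have a lower 95% limit of at least 50%. With 30% prevalence, 10.7 expects 45 CAD-positive subjects among 150, which leaves 105 CAD-negative.

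Two other places bear on the unenhanced level. Section 3 reports that studies of more than 100 patients "show a range for sensitivity of between 61–95"%, and gives 51–95% for specificity. Section 5.2 says that "8% of the UE-DSE images are expected to be unevaluable"; Table E in 10.6.1.2 scores such scans as errors in both truth classes.

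**The concern.** The two calculations concern the same parameter in the same subjects, and success needs both. Yet each uses its own input, and the plan never puts them side by side. If CE-DSE is 65% and the gain is 25 points, UE-DSE is 40% for both sensitivity and specificity. That is under the 50% that the plan itself treats as chance, and 21 and 11 points under the lower ends of the ranges in section 3.

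What is at stake is the meaning of the 80%. A reader of 10.7 will take it as the chance of success on the diagnostic endpoint, per reader and class. It covers only one of the two conditions, and the other is sized at a value of CE-DSE where it is met little more often than not.

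**Working it through.** **1. Reproduce the plan's figure.** Inputs from 10.7: two-sided alpha 0.05 (z = 1.960), power 0.80 (z = 0.8416), difference d = 0.25, discordance ψ = 0.40. The Miettinen formula for McNemar's test is

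n = [1.960·ψ + 0.8416·√(ψ² − d²(3+ψ)/4)]² / (ψ·d²)
= [0.784 + 0.8416·√0.106875]² / 0.025 = 44.87, i.e. 45.

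The stated 45 is reproduced. Full enumeration of the uncorrected McNemar chi-square at n = 45 gives power 80.4%.

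**2. What that power depends on.** The discordant cells are (0.40 + 0.25)/2 = 0.325 and (0.40 − 0.25)/2 = 0.075. The levels of UE-DSE and CE-DSE do not enter. Any feasible pair 25 points apart gives the same 80.4%, with UE-DSE anywhere from 7.5% to 67.5%.

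**3. The floor condition at 65%.** The Wald lower limit is 0.65 − 1.96·√(0.65·0.35/45) = 0.511. So an *observed* 65% clears 50%, as 10.7 says. A *true* 65% is a different matter. With n = 45 the Wald limit reaches 50% from 29 correct reads (29/45 = 64.4%, limit 0.505), and P(X ≥ 29 | 45, 0.65) = 59.8%. With Wilson or Clopper-Pearson limits, 30 are needed and the probability is 47.5%. Neither 10.6.1.2 nor 10.7 names the interval method for sensitivity and specificity.

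**4. The implied comparator.** UE-DSE = 65% − 25% = 40%. Both-correct cell: 0.40 − 0.075 = 0.325. Both-wrong cell: 1 − 0.325 − 0.075 − 0.325 = 0.275.

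**5. Both conditions together**, one reader and one truth class, by enumeration over the four cells (discordance 40%, Wald limit of at least 50%):

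| UE / CE | n | McNemar | Both conditions |
|---|---|---|---|
| 40 / 65 | 45 | 80.4% | 54.9% |
| 51 / 76 | 45 | 80.4% | 79.6% |
| 61 / 86 | 45 | 80.4% | 80.4% |
| 40 / 65 | 105 | 99.1% | 87.7% |
| 51 / 76 | 105 | 99.1% | 99.1% |

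**6. Sensitivity and specificity for one reader.** They come from different subjects, so for fixed class sizes the probabilities multiply. If both are required, 40/65 gives 0.549 × 0.877 = 48%. With 61/86 for sensitivity and 51/76 for specificity the product is 0.804 × 0.991 = 80%.

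**7. Is 40% below guessing?** With 8% unevaluable scans scored as errors, guessing on the rest scores 0.5 × 0.92 = 46%. Guessing falls to 40% if 20% are unevaluable (0.5 × 0.80), and to 35% if 30% are.

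**The case against.** The strongest reply is that 10.7 contains no arithmetic error. Both stated calculations reproduce, and 80% is the power of the scenario that it writes down: a 25-point gain with 40% discordance. This stands. A reader might infer from the 40% comparator that the 80% belongs to no scenario in the plan. The documents do not support that: step 2 shows that the figure holds at 40/65 and equally at 51/76 and 61/86, and the latter two use values inside the ranges in section 3.

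Secondly, the 65% may be meant only as a low enhanced value at which the interval still clears 50%, not as the expected value under superiority. The text leaves that open. But 10.7 introduces it as an assumption, gives no other CE-DSE level, and 10.6.4 ties the two conditions together.

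Thirdly, a reader might infer that a 40% comparator is impossible, or contradicts section 3. That goes too far. The published range is for DSE in general. This trial enrols only subjects with suboptimal unenhanced images at rest, reads them without clinical information, and counts unevaluable scans as errors. Under 8.6.3.3 an unevaluable score at either rest or stress makes the overall conclusion unevaluable, so if the 8% refers to stress images only, it may be too low for the overall diagnosis. Section 3 mentions up to 30% non-diagnostic or poor images, though not all of these would be unevaluable. So 40% is unexplained rather than excluded.

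Finally, one can hold CE-DSE at 65% and raise UE-DSE to 61%, which leaves a 4-point gain and about 6% McNemar power at 40% discordance. That abandons the planned gain and is not a scenario that the plan puts forward; it should not be quoted as the trial's power.

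**Conclusion.** The point holds in a limited form. Section 10.7 states no unenhanced level, no joint scenario and no joint power, although 10.6.4 requires superiority and the floor from the same readers. At the only pair that its two inputs jointly define, 40/65, the chance that one reader meets both sensitivity conditions with 45 CAD-positive subjects is about 55%, not 80%. The floor condition is the cause: at a true 65% it is met about 60% of the time with a Wald limit. With a Wilson or Clopper-Pearson limit it is met 47.5% of the time, which then caps the joint probability.

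A reader might conclude that the trial is underpowered. The documents do not show that. If the 25-point gain is on top of 51% or 61%, the joint probability is about 80% and the planned numbers suffice for one reader and one class.

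The figures assume 40% discordance, the uncorrected McNemar statistic, a Wald limit, and exactly 45 and 105 evaluable subjects. They are per reader. The two-of-three rule is not included; its effect depends on agreement between readers, for which the plan gives no value.

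**What to change.** In 10.7, replace the two separate inputs by one coherent scenario for sensitivity (n = 45) and one for specificity (n about 105). Each should state UE-DSE, CE-DSE, discordance and the confidence-interval method. Say that 80% is the power of the superiority test only, and add the joint power for the 10.6.4 rule. For sensitivity, per reader, that is about 55% at 40/65, or about 80% conditional on CE-DSE of roughly 76–86%. If the sponsor does expect UE-DSE near 40%, give the reason, for example the suboptimal-image population and the scoring of unevaluable scans. If 65% was meant only as a minimum enhanced value, say so and state the expected value as well.

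The cost is a rewording of 10.7. No subjects are added, and the analysis changes only in that the interval method is named. The drawback for the sponsor is a stated power that is lower, or that depends openly on a higher enhanced value.

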5.4 Study Population

The study will be conducted in subjects who have suboptimal image quality on UEUS echocardiography at rest and are scheduled for coronary angiography. It is expected that 10-15 study centers will participate in the study. Approximately 175 subjects will be enrolled in order to obtain 45 subjects with positive CAD and 45 with negative CAD based on the truth standard. The prevalence of positive CAD subjects will be tracked based on the onsite diagnosis of CAD from the truth standard. If the overall yield of positive CAD subjects is lower than the assumed

30%,³⁴ then additional subjects will need to be enrolled in order to obtain a sufficient number of positive CAD subjects.

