10.6.1.1 Truth Standard Diagnosis

For subjects with coronary angiography as the truth standard, a subject will be diagnosed by the blinded off-site coronary angiography reader as Positive if percentage diameter stenosis of any of the vessels (RCA, LAD, LCx and LM) is $\geq 50\%$; otherwise, a subject will be considered as Negative.

For the remaining subjects who didn't have coronary angiography as the truth standard, a subject will be Positive if the subject had cardiac death, documented myocardial infarction, documented

revascularization or need for revascularization during follow up; otherwise, the subject will be considered as Negative.

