10.6.1.2 Evaluation of CAD

The overall diagnostic echocardiographic conclusion will be classified by the off-site readers as Normal, Abnormal or Unevaluable for unenhanced (UEUS and UE-DSE) and LUMASON-enhanced (CEUS and CE-DSE) echocardiography respectively.

The diagnostic performance of echocardiography (UE-DSE and CE-DSE) will be derived based on the diagnosis from stress echocardiography and diagnosis from truth standard (see Table E).

Table E: Cross Tabulation of Diagnosis: Truth Standard vs. Stress Echocardiography

Truth Standard (TS)	Stress Echocardiography		
	Normal	Unevaluable*	Abnormal
Negative	TN	FP	FP
Positive	FN	FN	TP

TN = true negative; TP = true positive; FN = false negative; FP = false positive

*Unevaluable is defined as: inadequate visualization of segments comprising all coronary artery territories due to motion artifacts, lateral wall drop out, swirling or attenuation artifacts.

The null hypothesis is that there is no difference in sensitivity/specificity between CE-DSE and UE-DSE at peak stress; the alternative hypothesis is that CE-DSE is superior to UE-DSE in terms of higher sensitivity/specificity:

$$H_0: \text{Diag}_{\text{CE}} - \text{Diag}_{\text{UE}} = 0,$$

$$H_a: \text{Diag}_{\text{CE}} - \text{Diag}_{\text{UE}} > 0;$$

where Diag_{CE} and Diag_{UE} denote sensitivity/specificity for CE-DSE and UE-DSE at peak stress respectively.

The sensitivity and the specificity along with their 95% confidence intervals (CIs) will be calculated, and the difference in sensitivity/specificity will be tested using McNemar's Chi-square 2-sided test.

In addition, inter-reader agreement for the detection/exclusion of CAD for CE-DSE and UE-DSE will be evaluated by kappa statistic.

10.6.2 Co-Primary Efficacy Endpoint – Critical Shift of Subjects with Suboptimal Images to Adequate Images

The co-primary endpoint: The proportion of subjects with suboptimal images (≥ 2 adjacent segments with inadequate LV EBD in any of the 3 apical views) at UE-DSE converted to adequate images (reduction of suboptimal adjacent segments to obtain adequate images) at CE-DSE will be estimated along with the 95% CIs.

Additionally, the following supportive analyses will be performed:

- proportion of subjects with optimal images at UE-DSE to suboptimal (≥ 2 adjacent segments with inadequate LV EBD in any of the 3 apical views) at CE-DSE in terms of LV EBD visualization will be estimated along with the 95% CIs.

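### Enrolment is extended on the on-site CAD diagnosis but sensitivity is analysed on the off-site angiography read, so the trial could close short of 45 analysable positives without the rule acting

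*Combined protocol and SAP*

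**What the plan says.** **Enrolment rule.** Section 5.4 plans about 175 subjects so as to obtain 45 CAD-positive and 45 CAD-negative subjects by the truth standard. It then states: "The prevalence of positive CAD subjects will be tracked based on the onsite diagnosis of CAD from the truth standard". Section 10.7 repeats this: "The prevalence of positive subjects will be tracked based on on-site CAD diagnosis from the truth standard". In both sections, the condition for enrolling more subjects is a tracked prevalence below 30%.

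**Analysed label.** For subjects with angiography, Section 10.6.1.1 says "a subject will be diagnosed by the blinded off-site coronary angiography reader as Positive" when any of the four listed vessels has a stenosis of at least 50%. The remaining subjects are classed by cardiac events during follow-up, with no off-site reader. Section 10.2 limits the efficacy analysis to dosed subjects with peak-stress data for both UE-DSE and CE-DSE and a definite truth-standard result.

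**Why 45.** Section 10.7 assumes two-sided 5% significance, 80% power and a 25-point gain from contrast. It concludes: "the proportion of discordant pairs is 40%, 45 subjects will be needed for sensitivity/specificity respectively". The test in Section 10.6.1.2 is McNemar's "Chi-square 2-sided test".

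**From 45 to 175.** At 30% prevalence, 45 positives require 150 subjects. An allowance of about 15% for dropout brings this to about 175. Section 5.4.3 says that discontinued subjects are not replaced.

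**The concern.** The rule that protects the positive stratum watches a different label from the one analysed. Sites report CAD from their own reading of the angiogram, and the analysis then replaces that reading with the central one. Section 5.2 justifies the central reader partly by the variability among many unblinded on-site readers, so the plan itself expects some disagreement.

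The trigger is also a prevalence, not a count of analysable positives. Prevalence can stay at 30% on site while the modified ITD population holds fewer than 45 positives by the analysed standard. No section compares the two counts before enrolment closes.

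What is at stake is the sensitivity half of the first co-primary endpoint: the McNemar comparison and the requirement in Section 10.6.4 that the lower 95% limit be at least 50%. Specificity is not at risk, because 175 × 0.85 × 0.70 = 104 negatives are expected against 45 needed.

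**Working it through.** **Inputs from Section 10.7:** difference 0.25, discordant proportion 0.40, two-sided alpha 0.05, power 0.80, prevalence 0.30, dropout 0.15, CE-DSE sensitivity 0.65. **Assumed, because the documents give no value:** r, the ratio of off-site to on-site angiographic positives, taken from 0.80 to 1.10.

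**Step 1. Reproduce 45.** The discordant cells are (0.40 + 0.25)/2 = 0.325 in favour of CE-DSE and (0.40 − 0.25)/2 = 0.075 against. The number of discordant pairs m is binomial(n, 0.40). Given m, the number favouring CE-DSE, x, is binomial(m, 0.325/0.40). With y = m − x, reject when x > y and (x − y)²/m ≥ 3.84. Summing over all outcomes gives power of 79.4% at n = 44 and 80.4% at n = 45, so the plan's 45 reproduces with the uncorrected test. A normal approximation to unconditional power gives 77.4% at 45.

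**Step 2. Reproduce 150 and 175.** 45/0.30 = 150, and 150/0.85 = 176.5, so 177 against the stated approximate 175.

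**Step 3. Reserve at the plan's own figures.** With perfect agreement and dropout unrelated to CAD status, 175 × 0.30 × 0.85 = 44.6 analysable positives. The dropout allowance is fully used by dropout, and nothing is left for reclassification.

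**Step 4. Effect of a net change in label.** Start from 45 analysable on-site positives, all by angiography, and count whole subjects (rounded down). The last column is 0.65 − 1.96 × √(0.65 × 0.35/n), a Wald limit. Section 10.6.1.2 does not name the interval method for sensitivity.

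| r (assumed) | 45 × r | n | McNemar power | Lower limit at observed 65% |
|---|---|---|---|---|
| 1.10 | 49.5 | 49 | 84.0% | 0.516 |
| 1.00 | 45 | 45 | 80.4% | 0.511 |
| 0.95 | 42.75 | 42 | 77.1% | 0.506 |
| 0.90 | 40.5 | 40 | 74.7% | 0.502 |
| 0.85 | 38.25 | 38 | 72.1% | 0.498 |
| 0.80 | 36 | 36 | 69.2% | 0.494 |

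At 38 or fewer positives, an observed sensitivity equal to the plan's 65% no longer clears the 50% limit on this interval.

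**Step 5. Would the rule act?** With 175 enrolled, on-site prevalence exactly 30% and 15% dropout, the rule does not trigger. The on-site prevalence needed for 45 analysable positives is 45/(175 × 0.85 × r): 30.3% at r = 1, 33.6% at r = 0.90 and 37.8% at r = 0.80. Between 30% and those values, the trial falls short and no extension follows.

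**Step 6. Mixed truth standard.** If half the positives come from 6-month events, which are not re-read, r = 0.80 leaves 45 × (0.5 × 0.80 + 0.5) = 40.5 positives, so 40 and 74.7% power.

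**The case against.** The strongest reply concerns direction. A reader might infer that central reading will downgrade on-site positives and leave the trial underpowered. The documents do not say so. Section 5.2 speaks of variability among on-site readers, not of over-calling. With more negatives than positives, equal error rates push the count up. Take 150 evaluable subjects, all with angiography, of whom 45 are positive and 105 negative on site. If 5% flip each way (an assumption), the central count is 45 − 2.25 + 5.25 = 48. A net loss needs a downgrade rate more than 105/45 = 2.3 times the upgrade rate. This stands, and it makes the shortfall a possibility, not a forecast.

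Three other strong readings also go too far:

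- **That the below-30% rule is the only protection for the 45.** The 15% allowance also protects the evaluable count, although it leaves no room for reclassification.
- **That the trigger is a percentage of enrolled subjects.** Section 10.7 does not state the denominator, and the stated purpose of both sections is to obtain enough positives.
- **That no central read will exist until enrolment has closed.** The timing of angiography reads is not stated, and Section 8.6.5 defers details of image handling and presentation to a separate document. What can be said is that no stated rule uses those reads when deciding on enrolment.

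Tracking accrual on site reads, which arrive first, is a reasonable operational choice. It does not answer the point, because the final decision to close can still be checked against the analysed label.

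**Conclusion.** The concern holds as a gap in the enrolment rule. The label and quantity that trigger extension differ from those analysed, and expected analysable positives are 44.6 against a requirement of 45. A net downward reclassification would therefore take the positive stratum below its planned size with no extension triggered.

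The size depends on an assumed disagreement. Net losses of 5% to 20% cost roughly 3 to 11 points of power (80.4% down to 77.1% and 69.2%) if every positive comes from angiography, and less if some come from 6-month events. Net upward reclassification, or true prevalence sufficiently above 30%, removes the shortfall. The power figures are for one reader's sensitivity comparison under the plan's own difference and discordance. The change is worth making before enrolment closes, but the point does not show that the design is unsound.

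**What to change.** Amend Sections 5.4 and 10.7 together:

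1. Keep the planned enrolment of about 175, with at least 150 evaluable subjects, as a minimum.
2. Have the already-planned off-site angiography reader read in batches during enrolment.
3. Before closing enrolment, base the decision to extend on the number of modified ITD subjects who are Positive by the analysed truth standard (off-site read, or 6-month events where there is no usable angiogram), with a target of 45. This replaces on-site prevalence as the deciding quantity.

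The minimum in item 1 is needed because stopping on 45 positives alone could harm the critical-shift co-primary endpoint, which is sized on 150. If prevalence were 50% (an assumption), 45 positives would be reached at about 90 evaluable subjects. At the plan's 45% shift rate, the lower limit would be 0.45 − 1.96 × √(0.2475/90) = 0.347, below the required 35%. At 150 it is 0.370.

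The cost is small. No reader, procedure or visit is added, and the closing decision waits a little for central reads and follow-up outcomes. Counting truth-standard positives does not compare UE-DSE with CE-DSE, and the angiography reader is blinded to the echocardiographic results, so the change is consistent with Section 10.9, which plans no interim analysis.
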